#### 4.5 Cyclo (His-pro) (CHP) Concentration Evaluation

In a subset of subjects where residual serum and/or plasma are available after completion of study-required tests, CHP levels in blood may be measured for the change from baseline.

### 5. HYPOTHESES

The primary objective is to assess the dose-dependent efficacy of Cyclo-Z for the treatment of subjects with obese type 2 diabetes. The hypothesis of this study is set as follows.

The dose-dependent efficacy of Cyclo-Z will be demonstrated by identifying statistically significant difference in the change of HbA1c level and BW from baseline at Week 12 in Dose A, B, C, and D using one-way analysis of variance (ANOVA) methods. Specifically, all three experimental groups will be compared to the control group on the change: Dose A vs. D, B vs. D, and C vs. D.

$$H_0: \mu_A = \mu_B = \mu_C = \mu_D$$

$$H_1: \text{not } H_0$$

$\mu$ : the mean of the primary clinical efficacy variables by each of the four dose groups

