
Name of Sponsor/Company: NovMetaPharma Co., Ltd.	
Study Product: Cyclo-Z	
Protocol Number	NMP-CYZ-P2-001
Indication	Obese Type 2 Diabetes
	
bilateral oophorectomy) at least 6 months before randomization.
 
 
• Post-menopausal for at least 12 months prior to Screening.
 
• If sexually active, they should use oral contraceptives, double barrier contraception (e.g., condom with spermicide), intrauterine device, or other methods approved by the Sponsor.
 

Statistical Analysis	
This is a Phase 2 clinical trial to evaluate safety and explore the potential efficacy of the study drug. Therefore, the number of subjects was not based on formal statistical power considerations. In this clinical trial, a total of 64 subjects was deemed sufficient and will be enrolled and randomly assigned to be administered with 1 of 3 dose levels of Cyclo-Z or placebo.
 
The co-primary variables, the reduction in HbA1c levels from baseline at Week 12 and the reduction of body weight (BW) from baseline at Week 12, will be analyzed using (ANOVA) methods if the change is approximately normally distributed. If the change is markedly non-normally distributed then Wilcoxon rank sum tests will be used.
 
The continuous secondary efficacy variables will be analyzed with ANOVA or Wilcoxon rank sum tests, as appropriate. The categorical secondary efficacy variables will be analyzed with chi-square tests or Fisher's exact tests, as appropriate.
 
The continuous exploratory efficacy variables will be analyzed with ANOVA or Wilcoxon rank sum tests, as appropriate. The categorical exploratory efficacy variables will be analyzed with chi-square tests or Fisher's exact tests, as appropriate.
 
Safety variables will be summarized descriptively, by treatment group and visit. No formal statistical testing will be completed on the safety variables.

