### 5.3 Randomization

At Visit 2 (Week 0), subjects who meet the inclusion/exclusion criteria will be randomly assigned to receive placebo or 1 of 3 doses of Cyclo-Z in accordance with the randomization code, which will be generated by the Sponsor. Specifically, the subjects will be randomly assigned in a 1:1:1:1 ratio to the following:

- Dose A: Cyclo-Z containing 23 mg zinc plus 3 mg CHP – 16 subjects
- Dose B: Cyclo-Z containing 23 mg zinc plus 9 mg CHP – 16 subjects

- Dose C: Cyclo-Z containing 23 mg zinc plus 15 mg CHP – 16 subjects
- Dose D: Placebo – 16 subjects

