#### 8.1.3 Primary Efficacy Analyses

The change from baseline to Week 12 in HbA1c will be compared for the experimental groups versus the control group using analysis of variance (ANOVA) methods if the change is approximately normally distributed. If the change is markedly non-normally distributed then Wilcoxon rank sum tests will be used. Specifically, all three experimental groups will be compared to the control group on the change: Dose A vs. D, B vs. D, and C vs. D.

The change from baseline to Week 12 in BW will be compared for the experimental groups versus the control group using ANOVA methods if the change is approximately normally distributed. If the change is markedly non-normally distributed then Wilcoxon rank sum tests will be used.

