## 2. STUDY OBJECTIVE(S)

### 2.1 Primary Objective

The primary objective is to assess the dose-dependent efficacy of Cyclo-Z for the treatment of subjects with obese type 2 diabetes.

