### 9.3.3 Missing Post-Baseline Evaluation

Primary analysis of continuous efficacy endpoints will be analyzed based on observed data without imputation.

In the sensitivity analysis of primary and the secondary efficacy endpoints, missing continuous efficacy endpoints will be handled using the LOCF method.

In the LOCF method, post-baseline missing continuous endpoints will be imputed using the last observed value including baseline value. For example, if subject has all of the post-baseline values as missing, then all of the post-baseline values will be imputed using the observed baseline value.

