# 10. STATISTICAL ANALYSES

## 10.1 General Principles

Statistical analysis will be conducted after database is locked and performed using SAS software version 9.4 according to this SAP. If statistical analysis methods are changed, it will be described in the final clinical study report.

Continuous variables will be summarized with means, standard deviations, medians, 25th & 75th percentiles, minimums, and maximums. Categorical variables will be summarized with counts and percentages. P-values less than 0.05 will be considered statistically significant. No adjustments for multiple comparison will be made to the result presented in this study because this is a phase 2 clinical trial and it is not formally powered with statistical algorithms.

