### 10.5.1 Primary Efficacy Analyses

- The change of HbA1c level from baseline at Week 12 will be summarized with mean, standard deviation, median, 25th & 75th percentiles, minimum, and maximum, overall and by each of the four groups, separately. To identify statistically significant difference in the change of HbA1c level from baseline at Week 12 between the four groups, one-way ANOVA will be performed. The tests between the experimental groups and the control group will be performed using Dunnett's test. If the change variables are markedly non-normally distributed then Kruskal-Wallis test and Wilcoxon rank-sum test will be used respectively. Specifically, all three experimental groups will be compared to the control group on the change: Dose A vs. D, B vs. D, and C vs. D. Also, to identify statistical significant difference between baseline and Week 12, one-sample t-test (paired t-test) or Wilcoxon signed-rank test will be performed within each of the four groups.
- The change of BW from baseline at Week 12 will be summarized with mean, standard deviation, median, 25th & 75th percentiles, minimum, and maximum, overall and by each of the four groups, separately. To identify statistically significant difference in the change of BW from baseline at Week 12 between the four groups, one-way ANOVA will be performed. The tests between the experimental groups and the control group will be performed using Dunnett's test. If the change variables are markedly non-normally distributed then Kruskal-Wallis test and Wilcoxon rank-sum test will be used respectively. Specifically, all three experimental groups will be compared to the control group on the change: Dose A vs. D, B vs. D, and C vs. D. Also, to identify statistical significant difference between baseline and Week 12, one-sample t-test (paired t-test) or Wilcoxon signed-rank test will be performed within each of the four groups.
- Sensitivity analysis described below will be performed for the primary endpoints at Week 12:
  1. Summary statistics and ANOVA model for continuous endpoints using imputed data by LOCF, EAS.
  2. Primary summary and analysis method based on Per Protocol Set.

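### SAP 5 lets a four-group ANOVA stand as proof of dose-dependent efficacy, but that test ignores dose order, and no planned test isolates differences between the doses

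*SAP*

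**What the plan says.** SAP 2.1 gives the aim: "The primary objective is to assess the dose-dependent efficacy of Cyclo-Z". SAP 5 turns that into a decision rule: "The dose-dependent efficacy of Cyclo-Z will be demonstrated by identifying statistically significant difference in the change of HbA1c level and BW", across Doses A, B, C and D by one-way ANOVA. The null hypothesis is that all four means are equal; the alternative is simply that they are not.

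The pairwise comparisons are A vs D, B vs D and C vs D. Protocol 8.1.3 says "all three experimental groups will be compared to the control group on the change", and SAP 5 and 10.5.1 plan the same three, with Dunnett's test. For non-normal data, SAP 10.5.1 says: "If the change variables are markedly non-normally distributed then Kruskal-Wallis test and Wilcoxon rank-sum test will be used respectively". The remaining tests of the primary endpoints are paired tests within each arm. SAP 10.8 and 10.9 allow only optional analyses without outliers and unspecified post-hoc work.

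The arms are set out in Protocol 5.3, beginning with "Dose A: Cyclo-Z containing 23 mg zinc plus 3 mg CHP". B and C have the same 23 mg zinc with 9 and 15 mg CHP, and D is placebo, which Protocol 5.5 describes as inert. Each arm has 16 subjects.

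**The concern.** A one-way ANOVA asks whether any of the four means differ. It does not use the order of the doses or the direction of the differences. Differences among A, B and C do contribute to F, but they cannot be separated from an effect that all three active arms share against placebo.

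Nothing else in the plan fills the gap. There is no trend test, dose-response model, or comparison of A, B and C with one another. Dunnett's test does not supply one: C significant against placebo and A not significant does not show that C differs from A. Kruskal-Wallis is as blind to order as the F test.

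The design makes the mistake plausible. The active arms differ only in CHP, and Protocol 1.2 credits zinc alone with some effect on glucose control. A zinc effect common to A, B and C would satisfy SAP 5 with no CHP dose response at all. At stake is a conclusion of dose-dependence, tied to the primary objective, that the test cannot support and that could mislead later dose selection.

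**Working it through.** **Inputs.** From the documents: four arms, 16 per arm (Protocol 5.3, SAP 3.4.1), significance level 0.05 (SAP 10.1). The sample size has no power basis (Protocol 8.2, SAP 3.3), so there is no stated power, SD or effect to reproduce. Assumed: normal changes with unit SD, effects in SD units, and two-sided contrasts. Because SAP 9.3.3 says "Primary analysis of continuous efficacy endpoints will be analyzed based on observed data without imputation", I also use an assumed 13 complete subjects per arm.

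**Order and direction.** For one simulated data set, F was 5.2412 under all 24 relabellings of the four groups and again with every sign reversed.

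**F test when the three doses are equally effective.** Noncentrality is λ = n Σ(μᵢ − μ̄)². With A = B = C = d and D = 0, μ̄ = 0.75d, so Σ = 3(0.25d)² + (0.75d)² = 0.75d². Hence λ = 12d² at n = 16 (3 and 60 df, critical F 2.758) and 9.75d² at n = 13 (3 and 48 df, critical F 2.798).

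| d (SD) | λ, n = 16 | F rejects, n = 16 | F rejects, n = 13 |
|---|---|---|---|
| 0.5 | 3.00 | 26% | 21% |
| 0.6 | 4.32 | 36% | 29% |
| 0.8 | 7.68 | 60% | 50% |
| 1.0 | 12.00 | 81% | 71% |
| 1.2 | 17.28 | 94% | 87% |

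Each rejection would be reported as dose-dependent efficacy although the response is flat. A two-sided linear contrast across A, B and C rejects in 5% of these cases, or 2.5% if only the favourable direction counts. Kruskal-Wallis at 16 per arm rejects in 55% (0.8 SD) and 79% (1.0 SD) (5,000 simulations).

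**F test for ordered responses, n = 16.** For A/B/C/D = 0.33/0.67/1.0/0, μ̄ = 0.5 and λ = 16 × 0.5556 = 8.89, giving 67%. The reverse, 1.0/0.67/0.33/0, has the same λ and the same 67%. For 1.0/0.5/0/0, λ = 11.0 and power is 77%. At a maximum effect of 1.0 SD, a flat response (81%) therefore meets the SAP 5 rule more often than the rising one (67%).

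**Both endpoints required.** SAP 5 names HbA1c and BW together, and the Protocol Synopsis speaks of "The co-primary variables, the reduction in HbA1c levels from baseline at Week 12" alongside body weight. With the same flat effect on each and an assumed correlation of 0 to 0.6 (40,000 simulated trials), both F tests reject in:

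| Flat effect | n = 16 | n = 13 |
|---|---|---|
| 0.8 SD | 36–45% | 25–34% |
| 1.0 SD | 66–71% | 51–58% |

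**What a slope test would do.** For the contrast (−1, 0, +1) on A, B, C, noncentrality is (μ_C − μ_A)/√(2/n), with √(2/16) = 0.354. Power at n = 16, two-sided 0.05:

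| A/B/C/D (SD) | Noncentrality | Slope | F test | Jonckheere-Terpstra, A–C |
|---|---|---|---|---|
| 0.2/0.6/1.0/0 | 2.26 | 0.61 | 0.70 | 0.57 |
| 0.33/0.67/1.0/0 | 1.89 | 0.46 | 0.67 | not run |
| 0.6/0.9/1.0/0 | 1.13 | 0.20 | 0.72 | 0.18 |
| 0.8/0.96/1.0/0 | 0.57 | 0.09 | 0.75 | 0.08 |

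At n = 13 the slope has power 0.52 for the first pattern (F test 0.59) and 0.38 for the second. The 95% interval for C − A has half-width 2.000 × 0.354 = 0.71 SD at n = 16 and 2.011 × √(2/13) = 0.79 SD at n = 13.

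**Why placebo must stay out of the slope.** A linear trend over 0, 3, 9 and 15 mg is significant in the favourable direction in 64% of trials under a flat 1.0 SD response at 16 per arm. It would repeat the problem.

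**The case against.** The strongest reply is that this is one sentence in an exploratory trial without formal powering. Protocol 8.1.3 does not make the claim, and SAP 10.5.1 presents the ANOVA only as a test for differences among four groups. SAP 5 goes straight on to the comparisons with control and treats placebo as one of four dose groups, so it can be read as meaning efficacy by dose level. No estimate or efficacy test is wrong. Direction can be read from the group means and the Dunnett comparisons; under rising harm up to 1.0 SD, the chance of any significant Dunnett benefit is about 0.001. A slope test is also weak and will miss many real dose responses.

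Much of this stands. The direction criticism applies to the ANOVA rule, not to the whole plan. The rejection rates illustrate a logical point under assumed effects; they do not forecast this trial's error rate. The slope's low power is real, so adding it is optional. Dunnett's protection is also lost in the non-normal fallback, where the rank-sum tests are unadjusted.

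None of it rescues the sentence. Exploratory status excuses imprecision, not a conclusion that the test cannot deliver. Counting placebo as dose zero does not help, because D differs from A in zinc and CHP together, and a flat effect still meets the rule as written.

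**Conclusion.** The concern holds. The plan tests whether each dose beats placebo but not whether the effect changes with dose, yet SAP 5 attaches the dose-dependence conclusion to an F test that a flat response can satisfy. For one endpoint and assumed flat effects of 0.5 to 1.2 SD, the false claim would arise in 26% to 94% of trials at 16 per arm and 21% to 87% at 13. These figures rest on normality, equal variances and effect sizes that the documents do not give. The order-blindness of the test rests on none of them. The error is confined to the inferential claim, but that claim is the stated test of the primary objective, so it needs correcting before unblinding.

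**What to change.** In SAP 5, delete the statement that the ANOVA demonstrates dose-dependent efficacy. Say instead that it tests whether any group means differ, and that Dunnett's A, B and C vs D tests each CHP-plus-zinc dose against placebo. Then choose one option before unblinding.

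- **Option 1: test it.** For HbA1c and BW, prespecify one two-sided linear contrast across A, B and C (−1, 0, +1; 3, 9 and 15 mg are equally spaced) from the same model, as the test of CHP dose response within 3–15 mg. Use Jonckheere-Terpstra across A, B and C when the non-normal fallback applies. Claim dose-dependence only from this test and only in the favourable direction, and state whether the claim is made per endpoint or needs both.
- **Option 2: describe it.** Restate SAP 5 as efficacy of each dose against placebo. Report the C − A and B − A differences with 95% confidence intervals, and make no inferential dose-dependence claim.

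Under either option, state that a non-significant slope does not show absence of dose response, and that these four arms cannot separate zinc from the lowest CHP dose.

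The cost is SAP wording and no new data. Option 2 adds no test and is enough on its own, but its intervals will be wide. Option 1 adds one test per primary endpoint to a plan that says "No adjustments for multiple comparison will be made to the result presented in this study", and its power is modest for a linear response and low for a saturating one.

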### 6. DEFINITIONS

- **Baseline** is defined as the last non-missing measurement taken on Week 0.
- **Study day 1** is defined as the first IP dose date. For subjects who are randomized but not dosed after randomization, the study day 1 is defined as the date of randomization.
- **Study day** is defined as the number of days from study day 1.

Before study day 1: study day = (date of interest – date of study day 1)

On or after study day 1: study day = (date of interest – date of study day 1) + 1

Therefore, the day prior to study day 1 is -1.

- **Study drug exposure day** is defined as the number of days that subjects were on the study drug.
- **Age (years)** is calculated as follows, and is rounded down to an integer.

$$Age = \frac{Date\ of\ Informed\ Consent - Date\ of\ birth}{365.25}$$

- **Diabetes disease period (years)** is calculated as follows, and is rounded down to an integer.

$$Diabetes\ disease\ period = \frac{Date\ of\ Screening - Date\ of\ diagnosis^*}{365.25}$$

\*If the month and day of date of diagnosis are unknown, it will be converted into January, first day.

- **OGTT** of secondary endpoint is used glucose value at 2 hour after glucose intake.
- **TAFGC** is calculated as follows:

$$TAFGC = \frac{\sum_n [Glucose\ value\ at\ (n)\ hour\ in\ OGTT - Glucose\ value\ at\ 0\ hour\ in\ OGTT]}{6},$$

where  $n = 0.5, 1.0, 1.5, 2.0, 2.5, \text{ and } 3$

- **BMI (kg/m^2)** is calculated as follows:

$$BMI = \frac{Body\ Weight\ (kg)}{Height\ (m) \times Height\ (m)}$$

- **Compliance (%)** is calculated as follows:

$$compliance = \frac{Number\ of\ capsules\ taken}{Number\ of\ capsules\ should\ be\ taken\ in\ principle^*} \times 100$$

\*By visit:  $Date\ of\ Visit(n) - Date\ of\ Visit(n - 1)$ , where  $n=3, 4, 5, 6, 7, \text{ and } 8$

Overall:  $\sum_n (Date\ of\ Visit(n) - Date\ of\ Visit(n - 1))$ , where  $n=3, 4, 5, 6, 7, \text{ and } 8$

## 7. ANALYSIS SUBSETS

This study is planned to analyze in analysis subsets of four groups: Full Analysis Set, Efficacy Analysis Set, Per Protocol Set, and Safety Analysis Set. For efficacy analysis, the Efficacy Analysis Set will be considered primarily and the Per Protocol Set will be considered as supportive. The Safety Analysis Set will be used in the safety analysis.

### 7.1 Full Analysis Set

The Full Analysis Set (FAS) includes all subjects who were randomized in the study. Subjects will be analyzed according to their randomized treatment, regardless of the treatment received. Tabulations of subject

enrollment by site, subject disposition, analysis subsets, demographic and baseline characteristics including diabetes disease, past and present medical history, concomitant medication, and protocol deviations including major protocol deviations will utilize this analysis set.

## 7.2 Efficacy Analysis Set

The Efficacy Analysis Set (EAS) will be used to carry out the efficacy analyses of efficacy endpoints, which is a subset of the FAS consisting of subjects who received at least one dose of study medication and who had baseline and any post-baseline efficacy data. Subjects will be analyzed according to their randomized treatment, regardless of the treatment received. Analyses for efficacy endpoints will utilize this analysis set.

## 7.3 Per Protocol Set

All subjects valid for EAS who meet ALL the following criteria will be „valid per protocol“ (also called „valid for efficacy“):

- Complete at least 2 weeks of treatment after randomization.
- Have both baseline and at least 2 weeks of efficacy data.
- Subject did not have any significant violation after randomization.

Major protocol deviations that will potentially impact the primary analysis of efficacy endpoints at Week12 or violate GCP at site will be discussed and decided prior to the database lock and will be applied in per protocol analysis:

The following cases are excluded from the Per Protocol Set:

- Informed consent was not provided
- Subjects who were withdrawn/early terminated
- Subjects who have not met inclusion/exclusion criteria
- Subjects who received excluded concomitant medications
- Subjects who have major protocol deviations - all protocol deviations will be classified as major or minor under the discussion with Sponsor before database is locked.

Additional criteria maybe added prior to unblinding of the study database.

**The Per Protocol Set will be used to perform the sensitivity analysis on the primary, the secondary, and the exploratory efficacy endpoints.**

## 7.4 Safety Analysis Set

The Safety Analysis Set will consist of all randomized subjects who received at least one dose of study medication and had any post-randomization safety data collected will be included in the evaluation of safety. Analyses of demographic and baseline characteristics, safety endpoints and summary of study medication administration will utilize this analysis set.

## 8. INTERIM ANALYSIS

No interim analyses are planned for this Phase 2 study.

## 9. DATA SCREENING AND ACCPETANCE

### 9.1 General Principles

The objective of data screening is to assess the quantity, quality, and statistical characteristics of the data relative to the requirements of the planned analyses. The Bio-statistics associate (BSA) who is in charge of this study will check errors of raw data prior to the beginning of data analysis.

### 9.2 Data Handling and Electronic Transfer of Data

After database is locked, a raw data validated by using Microsoft Structured Query Language (MsSQL) will be directly accessed using SAS Open Database Connectivity (ODBC) Driver. The raw data needed for analysis will be transferred from Database Management System (DBMS) to standard folder to store the raw data on the server via SAS ODBC, and the analysis dataset will be created in „DATASET“ folder. The analysis dataset will be generated using SAS software version 9.4 according to analysis dataset specification created in accordance with this SAP.

### 9.3 Handling of Missing and Incomplete Data

If subjects either discontinues from the clinical trial or the outcome measurement at any point is missing post-baseline, then the missing data will be imputed from the last measured outcome value using the Last Observation Carried Forward (LOCF) method.

#### 9.3.1 Missing and Incomplete Dates

Missing or incomplete dates will be listed as it is in any listings.

Incomplete start date of an adverse event or concomitant medication taken will be handled by following rule:

Start Date	Missing	Imputation	Exception
Adverse Event Concomitant Medication	Day	01	Default to Study Day 1 if an AE starts at the same year and month as Study Day 1 and the flag indicates that the AE started on or after the first dose on the AE CRF
	Day/Month	01JAN	Default to Study Day 1 if an AE started at the same year as Study Day 1 and the flag indicates that the AE started on or after the first dose on the AE CRF
	Day/Month/Year	No Imputation	

